## **TARGET ACCRUAL AND STUDY DURATION**

A maximum of 50 subjects [Part I (10 patients) and Part II (40 patients)] will be enrolled. The number of subjects required is a function of the expected feasibility. Accrual is expected to take up to 2.5 years.

## **5 SUBJECT SELECTION**

Patients who are scheduled to undergo surgical resection in the operating room who can provide informed consent, have a good performance status (ECOG  $\leq 2$ ), and have no known allergy or prior reaction to fluorescein, are eligible.

### **5.1 INCLUSION CRITERIA**

1. Age  $\geq 18$  years of age.
2. Have an ECOG Performance Status of  $\leq 2$ . Refer to Appendix B.
3. Have measurable tumor by direct visualization (visible lesion typically  $> 0.5$  cm in maximal diameter).
4. Deep space tumor that meets indications for resection.
5. Subject must understand the investigational nature of this study and sign an Independent Ethics Committee/Institutional Review Board approved written informed consent form prior to receiving any study related procedure.
6. A negative skin-prick test to fluorescein.

### **5.2 EXCLUSION CRITERIA**

1. Uncontrolled intercurrent illness including, but not limited to, ongoing or active infection, symptomatic congestive heart failure, unstable angina pectoris, cardiac arrhythmia, or psychiatric illness/social situations.
2. Renal dysfunction as defined as a GFR  $< 45$ .
3. Liver dysfunction as defined by Child-Pugh score  $> 5$ , or LFT's 1.5x above normal range.
4. Any known allergy or prior reaction to fluorescein or a positive skin prick test to fluorescein.
5. Pregnant or nursing female subjects, determined preoperatively with a urine pregnancy test.

- |   |
|---|
| 6. Unwilling or unable to follow protocol requirements.   |
| 7. Any condition which in the Investigators' opinion deems the patient unsuitable (e.g., abnormal EKG). |
| 8. Any condition that excludes surgical resection as the standard of care for the patient.              |

### **5.3 INCLUSION OF WOMEN AND MINORITIES**

Both men and women and members of all races and ethnic groups are eligible for this study.

### **5.4 SUBJECT WITHDRAWAL**

Any time prior to the planned surgical procedure, the patient may withdraw from this observational study for any reason without prejudice.

## **6 STUDY PROCEDURES**

### **6.1 BASELINE EVALUATIONS**

Standard presurgical assessment with labs and studies as determined by the preoperative Anesthesia clinic based upon their established guidelines.

The following will be performed within 1-4 weeks prior to the planned microscopic observation:

- Informed consent: Must be completed prior to receiving any study-related procedures.
- Medical history
- Physical examination, including vital signs (i.e., temperature, heart rate, respiratory rate, blood pressure, body weight, and height).
- If determined to be eligible for the study and after giving informed consent, a skin-prick test to determine sensitivity and risk of anaphylaxis to fluorescein will be performed by the Principal Investigator. For testing allergic response to fluorescein, a sterile Duotip® lancet (Lincoln Medical, USA) is used in 2 separate areas of skin on the forearm. The skin-pricks will include approximately 4 microliters of 10% or 25% fluorescein administered in areas of skin prepped with an alcohol pad. After 30 minutes, the appearance of a wheal greater than 3 mm in diameter is considered a positive test result. If a positive test is noted, the patient will no longer be eligible for this study. For comfort and relief of any skin irritation/pruritis, the patient will be offered an anti-histamine (fexofenadine [Allegra®] 30 mg po x 1) following the skin-prick test if necessary.
- If indicated by anesthesia pre-op assessment (standard operating procedure for pre-op clinic)
  - Hematology [i.e., CBC (with or without differential, auto or manual), ANC, and platelets].

- A complete metabolic panel (CMP): chloride, Co2, potassium, sodium, BUN, glucose, calcium, creatinine, total protein, albumin, total bilirubin, alkaline phosphatase, AST, ALT, A/G ratio, BUN/creatinine ratio, osmol (Calc), anion gap).
- If indicated by anesthesia pre-op assessment (standard operating procedure for the pre-op clinic) – 12-lead electrocardiogram, chest x-ray, and/or pulmonary function tests if indicated. These tests are not strictly required to support eligibility for this study, but if indicated and performed, may exclude the patient from receiving a general anesthetic and therefore, a wide excision performed in the operating room (thereby excluding the patient from this study).
- Pregnancy test (urine) in females of childbearing potential. Females who have undergone surgical sterilization or who have been postmenopausal for at least 2 years are not considered to be of childbearing potential. The standard operating procedure for all females of childbearing potential is to obtain a urine HCG (or a serum HCG if urine unable to be obtained). If the pregnancy test is positive, the patient is excluded from the study.

## 6.2 EVALUATIONS PERFORMED AT END OF TREATMENT

- Standard Post Anesthesia Care Unit (PACU) protocols for patient recovery from surgery. Patients will be continuously monitored for any reaction to fluorescein both intraoperatively and during the recovery period. Adverse events will be recorded throughout the time of entry into the operating room until the post-operative follow up. If the patient is transported directly to the Intensive Care Unit (ICU), these protocols will also be performed.

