## **1.1 DIAGNOSTIC INTERVENTION - FLUORESCEIN**

Drug Information - Fluorescein is delivered intravenously during the course of this observation. Fluorescein is an FDA approved drug for visual angiography. The package insert is shown in Appendix A. A single dose consists of a 5 mL vial of 10 or 25% fluorescein and costs \$3.90.

Fluorescein has a very rare incidence of anaphylactic reaction (1 in 222,000), but a skin-prick test may allow these patients to be recognized.[14] Therefore, any reported sensitivity to fluorescein will be considered an exclusion criteria as well as a positive skin-prick test performed during the routine preoperative visit (at least 1 week prior to surgery). The skin-prick test will be performed at the time of the preoperative visit if the patient decides to enter the clinical trial and signs the informed consent. Patients that are not eligible for the study or do not give consent to participate in the study will not undergo a skin-prick test.

The skin-prick test will be performed by the Principal Investigator using a sterile Duotip® lancet (Lincoln Medical, USA) in 2 separate areas of skin on the forearm. The skin-pricks will include 4 microliters of 10% fluorescein administered in areas of skin prepped with an alcohol pad. After 30 minutes, the appearance of a wheal greater than 3 mm in diameter is considered a positive test result. If a positive test is noted, the patient will no longer be eligible for this study. For comfort and relief of any skin irritation/pruritis, the patient will be offered an anti-histamine (fexofenadine [Allegra®] 30 mg po x 1) following the skin-prick test if necessary.

The package insert for fluorescein (which is a commonly used agent in the OR and readily available to the anesthesiologist in their PYXIS system and does not require delivery from pharmacy or an order to pharmacy) is attached in the Appendix section.

The fluorescein will be provided by the study. It will be ordered and sent to surgery for the patient at the time of the planned microscopic observation.

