## 6.3 POST-TREATMENT FOLLOW-UP EVALUATIONS

- Standard follow-up and safety evaluations from surgery includes a post-op visit at 2-3 weeks and scheduled follow-up based upon final staging of the patient's cancer. Follow-up will be based upon current NCCN guidelines.

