## 7 SAFETY EVALUATION

### 7.1 ADVERSE EVENTS

#### 7.1.1 DEFINITION

An adverse event or adverse experience (AE) is any untoward medical occurrence associated with the use of a drug in humans, whether or not considered drug related. Therefore, an AE can be **ANY** unfavorable and unintended sign (including an abnormal laboratory finding), symptom,

or disease temporally associated with the use of a medicinal (investigational) product, whether or not considered related to the medicinal (investigational) product (attribution of ‘unrelated’, ‘unlikely’, ‘possible’, ‘probable’, or ‘definite’).

An AE is considered “unexpected” if it is not listed in the investigator brochure or is not listed at the specificity or severity that has been observed; or if an investigator brochure is not required or available, is not consistent with the risk information described in the general investigational plan in other study-related documents. “Unexpected” also refers to adverse events that are mentioned in the investigator brochure (or other study-related documents) as occurring with a class of drugs or as anticipated from the pharmacological properties of the drug, but are not specifically mentioned as occurring with the particular study drug.

Adverse events will be recorded in this study for the purpose of safety monitoring and adverse events are anticipated to be absent or unlikely.

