### 7.1.3 REPORTING ADVERSE EVENTS

**Table 1. Guidelines for Routine Adverse Event Reporting for Pilot Studies (Regardless of Expectedness)**

Attribution	Grade 1	Grade 2	Grade 3	Grade 4	Grade 5
Unrelated	X	X	X	X	X
Unlikely	X	X	X	X	X
Possible	X	X	X	X	X
Probable	X	X	X	X	X
Definite	X	X	X	X	X

All subjects are evaluated at baseline and any abnormalities are documented.

- Worsening abnormalities and/or worsening of a pre-existing condition (e.g., diabetes, migraine that has increased in severity, frequency or duration of the condition, or an association with significantly worse outcome) can become an AE or serious adverse event and must be documented and followed.
- A persistent AE is one that extends continuously, without resolution between treatment cycles/courses. Reporting of persistent AEs is as follows:
  - a) Routine reporting: The AE must be reported only once unless the grade becomes more severe in a subsequent cycle/course. If the grade becomes more severe the AE must be reported again with the new grade.
  - b) Expedited Reporting: the AE must be reported only once unless the grade becomes more severe in the same or a subsequent cycle/course.
- A recurrent AE is one that occurs and resolves during a cycle/course of therapy and then reoccurs in a later cycle/course. Reporting of recurrent AEs is as follows:
  - a) Routine Reporting: An AE that resolves and then recurs during a subsequent cycle/course must be reported by the routine procedures.
  - b) Expedited Reporting: An AE that resolves and then recurs during a subsequent cycle/course does not require reporting unless the grade increases and hospitalization is associated with the recurring AE.
- At each evaluation, the Investigator will determine whether any AEs have occurred by evaluating the subject's signs, symptoms, and current laboratory and/or other test results.
- All AEs (expected or unexpected), including worsening of a pre-existing conditions (increased severity, frequency or duration of the condition and/or associated with significantly worse outcomes) which occur during the specified collection period, whether observed by the Investigator or by the subject, and whether or not thought to be related to study drug, will be documented in detail and followed until resolution, stabilization, death, or the start of new treatment.

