## 7.2 SERIOUS ADVERSE EVENTS

### 7.2.1 DEFINITION

A serious adverse event (SAE) is any adverse event (experience) that in the opinion of either the investigator or sponsor results in **ANY** of the following:

- Death.
- A life-threatening adverse event (experience). Any AE that places a subject or subject, in the view of the Investigator or sponsor, at immediate risk of death from the reaction as it occurred. It does **NOT** include an AE that, had it occurred in a more severe form, might have caused death.
- Inpatient hospitalization or prolongation of existing hospitalization (for > 24 hours).
- A persistent or significant incapacity or substantial disruption of the ability to conduct normal life functions.
- A congenital anomaly or birth defect.
- Important Medical Event (IME) that, based upon medical judgment, may jeopardize the subject or subject and may require medical or surgical intervention to prevent one of the outcomes listed above.

Elective hospital admission (including planned treatment for progressive disease or a planned protocol procedure), admission for socioeconomic reasons, and death due to tumor progression will not be considered an SAE.

All SAEs will be collected from the date of subject or subject signing consent until 30 days after the last dose of study drug and/or procedure.

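### Adverse event recording opens at operating-room entry, so non-serious reactions to the earlier, study-only fluorescein skin-prick test fall outside the only stated AE window

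*Combined protocol and SAP*

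**What the plan says.** Two collection windows are stated.

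- **AEs in general (Section 6.2):** "Adverse events will be recorded throughout the time of entry into the operating room until the post-operative follow up". Section 6.3 describes follow-up that "includes a post-op visit at 2-3 weeks".
- **SAEs (Section 7.2.1):** "All SAEs will be collected from the date of subject or subject signing consent until 30 days after the last dose of study drug" or the procedure.

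The skin-prick test comes before the operating room. Section 1.1 has it "performed during the routine preoperative visit (at least 1 week prior to surgery)", and Section 6.1 puts it one to four weeks before the microscopic observation. Section 1.1 also makes clear that patients who are ineligible or decline consent do not have it, so it is a study procedure and not routine care. Sections 1.1 and 6.1 both foresee local irritation or itching afterwards and offer an antihistamine. A wheal over 3 mm is a positive test and ends eligibility.

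Section 7.1.1 defines an AE as "any untoward medical occurrence associated with the use of a drug in humans", which is broad enough to include a reaction to the test. Section 7.1.3 asks for all grades and attributions, but confines documentation to AEs "which occur during the specified collection period". It also says: "At each evaluation, the Investigator will determine whether any AEs have occurred".

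Section 9 plans AE and complication rates with upper one-sided 95% Clopper-Pearson limits. It does not name the exposure, the period or the denominator.

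**The concern.** The skin test is each participant's first study exposure to fluorescein. Section 1.2 names allergic reaction to fluorescein as the trial's one added risk, and Section 1.1.2 notes that sensitization can grow with repeated use. A patient who itches, or has a wheal of 3 mm or less, tests negative and goes on to intravenous fluorescein. Section 4.2 allows a second intravenous dose after a fluid bolus or vasopressor. Under Section 6.2 as written, the earlier reaction need not be entered as an AE.

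Two things are at stake. One is the safety record: a stated rule, if followed, leaves out non-serious events that the protocol itself anticipates. The other is the meaning of the Section 9 rates. A reader could take them as the rate of reactions to fluorescein in this trial, although they may leave out one of the exposures. The plan also does not say whether patients who test positive and leave count in any AE denominator.

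**Working it through.** **1. Order of events**

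| Step | Timing | Source | AE window open? | SAE window open? |
|---|---|---|---|---|
| Consent | Before any study procedure | 6.1 | No | Yes |
| Skin-prick test | 1-4 weeks before observation | 6.1; 1.1 says at least 1 week before surgery | No | Yes |
| Operating-room entry, IV fluorescein | Day of surgery | 4.2, 6.2 | Yes | Yes |
| Post-operative visit | 2-3 weeks | 6.3 | Closes | Yes |
| 30 days after last dose or procedure | Day 30 | 7.2.1 | No | Closes |

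The test therefore precedes the AE window by at least a week. A serious reaction to it is captured; a non-serious one is not, if the collection period in Section 7.1.3 means the window in Section 6.2. No other general AE window is given.

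**2. Planned figure**

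The plan gives no expected AE rate or AE confidence limit, so there is none to reproduce. The planned limit for k patients with an AE out of n is

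U = 0.95 quantile of Beta(k + 1, n − k).

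For k = 0 this is U = 1 − 0.05^(1/n). With the maximum n = 50 (Section 9), U = 1 − 0.05^(1/50) = 5.8%.

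**3. Illustration of size**

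The documents give no number of skin-test reactions. Let m be an assumed number of enrolled patients who have such a reaction and no other counted AE. Each adds 1/50 = 2 points to the rate.

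| m | From 0/50: rate (upper limit) | From 5/50: rate (upper limit) |
|---|---|---|
| 0 | 0% (5.8%) | 10% (19.9%) |
| 1 | 2% (9.1%) | 12% (22.3%) |
| 3 | 6% (14.8%) | 16% (27.0%) |
| 5 | 10% (19.9%) | 20% (31.6%) |

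The first added patient moves the limit by 9.1 − 5.8 = 3.3 points from a base of 0/50, and by 22.3 − 19.9 = 2.4 points from 5/50.

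If the m patients instead tested positive and never reached surgery, they would enter both numerator and denominator. From 0/50 this gives 1/51 = 2.0% (9.0%), 3/53 = 5.7% (14.0%) and 5/55 = 9.1% (18.2%).

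**4. When nothing changes**

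If the Section 9 rate is defined as events during or after HIVM among patients who undergo it, skin-test reactions do not belong in it and the rate is unaffected. A per-patient rate is also unaffected by any reactor who has another counted AE.

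**5. End of the windows**

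Counting from a dose given at surgery, AE recording can stop 30 − 21 = 9 to 30 − 14 = 16 days before SAE collection does.

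**The case against.** A reader might infer that skin-test reactions are never counted and that the AE rates are therefore too low. The documents do not support either statement at that strength.

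- **Not certainly uncounted.** Section 7.1.3 has baseline abnormalities documented and AEs assessed at every evaluation, which could include the pre-operative visit. Whether the wheal exceeds 3 mm is determined for every patient as an eligibility item, and serious reactions are collected from consent. What may be lost is mainly minor local irritation. This objection stands in part: the wording is ambiguous, but the tie to a specified collection period, with an explicit start in Section 6.2, favours exclusion.
- **Bias not shown.** Section 9 leaves the exposure and denominator undefined. If the rates describe HIVM alone, there is no understatement. This stands.
- **The base of 0/50 flatters the effect.** These are surgical resections, and every AE grade and attribution is reportable, so 50 patients with no other AE is an unlikely starting point. This stands; the figures above are illustrations and fit a fluorescein-related rate best.
- **Pooling would be poor practice.** The prick uses about 4 microliters against 1-2 mL per intravenous dose, a volume 250 to 500 times smaller. Mixing prick-site itch with systemic reactions would blur the rate. This stands, and is why separate reporting is recommended.
- **The closing dates matter little.** Section 1.1.2 has the dye eliminated within 24 to 36 hours, and a shorter window for AEs than for SAEs is not in itself an error. This stands.
- **A document is not to hand.** The Data Safety Monitoring Plan is held with the IRB (Section 8) and may set AE collection rules. That limits confidence but does not remove the conflict within the protocol.

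**Conclusion.** The gap holds in a limited form. The only stated general AE window opens after a study-only fluorescein exposure, while the SAE window opens before it. On the more natural reading of Section 7.1.3, non-serious skin-test reactions are left out of the AE record.

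Any effect on the Section 9 rates is conditional. They may be understated if they are meant to cover all fluorescein exposure, and only through patients who react to the test and have no other counted AE. The number of such patients is not in the documents, so the size cannot be determined. The scale is 2 points on the rate and about 2 to 3 points on the upper limit per such patient, assuming 50 patients.

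The different end dates are a minor inconsistency and are not shown to bias any result. The primary endpoint, the feasibility rule and the sample size are unaffected.

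**What to change.** - **Section 6.2:** start AE recording at consent, matching the SAE start in Section 7.2.1, or at the skin-prick test. State in Section 7.1.3 that this is the collection period it refers to.
- **Section 9, skin test:** report skin-test reactions on their own, with all patients tested as the denominator, including those who test positive and leave the study.
- **Section 9, intraoperative period:** define the AE and complication rates as those of the intravenous fluorescein/HIVM period among patients who undergo it, and name that denominator for the Clopper-Pearson limits.
- **Sections 6.2 and 7.2.1:** reconcile the two closing dates, or state that the difference is intended.

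The cost is a wording amendment and a few eCRF entries at a visit that already takes place, where the test is already read at 30 minutes. Patients who test positive would need a short AE record before leaving the study.

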## 6.3 POST-TREATMENT FOLLOW-UP EVALUATIONS

- Standard follow-up and safety evaluations from surgery includes a post-op visit at 2-3 weeks and scheduled follow-up based upon final staging of the patient's cancer. Follow-up will be based upon current NCCN guidelines.

### Study Calendar

	Pre-operative Visit	Surgery	Post-operative Visit
History and Physical	X		
Informed consent	X		
Fluorescein skin prick test	X		
Tests as medically indicated	X		

Surgical resection with IVM		X	
Post-surgical monitoring in recovery and inpatient stay		X	
Review of pathology			X
Routine cancer surveillance			X

- At the completion of the surgery, if gross tumor is entirely debulked (R0 resection), then patients are considered disease free. Treatment response will be based upon the presence of a recurrence of tumor at either the primary site, locoregional recurrence (peritoneum), or metastatic sites.
- The time to recurrence will determine the standard length of clinical follow up. However, for this study, a 10-year limit will be placed on clinical data collection during the standard clinical follow up. After a patient is enrolled, the duration of data collection will end at 10 years from the time of microscopic observation (surgery). These data (time of recurrence and/or survival) will be correlated with findings from the one-time, initial IVM observation for the defined 10-year period of data collection.
- The surveillance data (no evidence of disease, disease recurrence, death) will be stored in a secured database and matched to the microscopic observation data. These data will serve as the basis for statistical comparisons of microscopic findings and clinical outcomes to be performed by our study statistician as described in section 9.

## 6.4 PATHOLOGY

Standard pathologic evaluation (no deviation from current standard practice of pathology department) will be performed.

## 7 SAFETY EVALUATION

### 7.1 ADVERSE EVENTS

#### 7.1.1 DEFINITION

An adverse event or adverse experience (AE) is any untoward medical occurrence associated with the use of a drug in humans, whether or not considered drug related. Therefore, an AE can be **ANY** unfavorable and unintended sign (including an abnormal laboratory finding), symptom,

or disease temporally associated with the use of a medicinal (investigational) product, whether or not considered related to the medicinal (investigational) product (attribution of ‘unrelated’, ‘unlikely’, ‘possible’, ‘probable’, or ‘definite’).

An AE is considered “unexpected” if it is not listed in the investigator brochure or is not listed at the specificity or severity that has been observed; or if an investigator brochure is not required or available, is not consistent with the risk information described in the general investigational plan in other study-related documents. “Unexpected” also refers to adverse events that are mentioned in the investigator brochure (or other study-related documents) as occurring with a class of drugs or as anticipated from the pharmacological properties of the drug, but are not specifically mentioned as occurring with the particular study drug.

Adverse events will be recorded in this study for the purpose of safety monitoring and adverse events are anticipated to be absent or unlikely.

